#### Table 1. Participants for lab test

#### Table 2. Participants for field trials

Prima	ary end user	s (SMCI)	Secor	ndary end users ( caregivers)	informal	Secondary (centres)	Control group		
Italy	Switzerland	Norway	Italy	Switzerland	Norway	All pilot sites			
20- 22	20-23	8-10	20-22	20-23	8-10	≥2	≥30 (≥10 per each pilot site)		

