The field trial is a pilot study, that is, a small-scale study, conducted mainly to control whether and how the developed services are perceived useful and usable. The defined qualitative and quantitative key performance indicators (KPI) will be evaluated and used to assess the degree to which engAGE meets the elders' needs, wishes and priorities in all trial sites (i.e. achieving better engagement, better social interaction, and accurate measurement of cognitive decline based on machine learning techniques). The measurements collected from the real-life trials will be elaborated and evaluated, to assess the ecosystem performance and validate the success of the project-developed technologies. The field trial will conduct only a partial evaluation of the effectiveness of services in relation to some dimensions of cognitive status of older people with MCI.

In the following scheme (Fig. 2) the study design is summarized. A certain number of people are recruited for the study, then those who do not meet the criteria or decline the participation are excluded. The remaining participant are randomly assigned to the experimentation group or to the control group. In randomization technique based on a single sequence of random assignments is used. A list of random numbers generated by the computer is used and subject is assigned a number based on their order of inclusion in the study. According to this technique, the 80 subjects are randomly assigned to the

experimentation group or to the control group. Then, for both the groups it has to be taken note of who loose follow up, discontinued intervention, and/or are excluded from analysis.

Figure 2. Field trial - study design

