#### 3.4 Outcomes

In this section the outcomes measured throughout the field trials are reported. The main focus of the engAGE project, and so of the field trial, is the perceived stability of cognitive capabilities of people with MCI. In second place, the acceptance and the usability of the platform, as well as the caregivers' benefits have to be assessed. Thus, the outcomes are the following:

- PRIMARY END USERS (SMCI):
  - Primary outcome: perceived stability of cognitive status (MAC-Q)

- Secondary outcomes: Adherence to intervention, wellbeing, quality of life, acceptance and usability, cost-benefit analysis
- SECONDARY END USERS (INFORMAL CAREGIVERS):
  - Reduction/stability of informal caregiver's burden
  - Improvement of well-being, psychological status
  - Acceptability, usability and affordability of the solution
- TERTIARY END USERS (FORMAL CAREGIVERS):
  - Improving quality of work.

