The **Warwick-Edinburgh Mental Wellbeing Scales (WEMBS)** [12] is used to enable the measuring of mental wellbeing in the general population. The 14-item scale WEMWBS has 5 response categories, summed to provide a single score. The items are all worded positively and cover both feeling and functioning aspects of mental wellbeing, thereby making the concept more accessible. The scale has been widely used nationally and internationally for monitoring, evaluating projects and programmes and investigating the determinants of mental wellbeing.

The **Unified Theory of Acceptance and Use of Technology (UTAUT)** [7] is a 20-item questionnaire that examines the acceptance of technology, determined by the effects of performance expectancy, effort expectancy, social influence and facilitating conditions.

The **Quality of Life – Alzheimer's Disease (QoL-AD)** [13] uses a scale of 1–4 (poor, fair, good, or excellent) to rate a variety of life domains, including the patient's physical health, mood, relationships, activities, and ability to complete tasks.

The **Zarit Burden Interview (ZBI)** is a caregiver self-report measure [9], containing 22 items. Each item on the interview is a statement which the caregiver is asked to endorse using a 5-point scale. Response options range from 0 (Never) to 4 (Nearly Always).

The **System Usability Scale (SUS)** [8] is a reliable tool for measuring usability. It consists of a 10-item questionnaire with five response options for respondents, from 'Strongly agree' to 'Strongly disagree'. It allows for evaluation of a wide variety of products and services, including hardware, software, mobile devices, websites and applications. It is easy to administer to participants and can be used on small sample sizes with reliable results and can effectively differentiate between usable and unusable systems.

Finally, a **semi-structured Interview** to evaluate the formal/informal caregivers' perspective on acceptability, usability and demand & cost information is built ad hoc, as the interview for the SMCI on usability and acceptability.

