#### 3.6.1 The control group

The control group (CG) will be given a booklet containing some suggested activities to do at home.

They will be evaluated at T0 and at T6 like the EG.

A first and a final meeting will take place in order to introduce and explain the project to the volunteers, and to show the results collected during the experimentation.

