#### 3.7 Work hypothesis

#### Work hypothesis

In this section, the hypothesis is presented along with solutions to measure the impact on those aspects.

- 1. Is there any improvement in the cognitive status?
  - Comparison of MAC-Q (before and after)
    - between groups (EG Vs CG)
    - o intra-group (EG)
- 2. Is the system usable for people with MCI?
  - Analysis of SUS in the EG
  - Analysis of UTAUT in the EG
  - stratifying for MCI
- 3. Is it the system effective in supporting lifestyle of people with MCI and their carers?
  - Adherence to the system to be assessed technically:
    - $\circ \quad \text{Nr. of interactions}$
    - o Nr. planned activities respected
- 4. And the quality of life of the participants?

- Comparison of QoL and WEMBS (before and after)
  - between groups (EG Vs CG)
  - o intra-group (EG)
- For Carers: Comparison of QoL and ZARIT (before and after)
  - between groups (EG Vs CG)
  - o intra-group (EG)
  - improvement of quality of work for Formal carers (from semi structured interview)
- 5. From semi-structured interview:
  - analysis of single modules' effectiveness/perception;
  - cost-benefit analysis;
  - willingness to pay.

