### ZARIT BURDEN INTERVIEW

- 0: NEVER
- 1: RARELY
- 2: SOMETIMES
- 3: QUITE FREQUENTLY
- 4: NEARLY ALWAYS

Please circle the response the best describes how you feel.

Qu	estion		s	coi	е	
1	Do you feel that your relative asks for more help than he/she needs?	0	1	2	3	4
2	Do you feel that because of the time you spend with your relative that you don't have enough time for yourself?	0	1	2	3	4
3	Do you feel stressed between caring for your relative and trying to meet other responsibilities for your family or work?	0	1	2	3	4
4	Do you feel embarrassed over your relative's behaviour?	0	1	2	3	4
5	Do you feel angry when you are around your relative?	0	1	2	3	4
6	Do you feel that your relative currently affects our relationships with other family members or friends in a negative way?	0	1	2	3	4
7	Are you afraid what the future holds for your relative?	0	1	2	3	4
8	Do you feel your relative is dependent on you?	0	1	2	3	1
9	Do you feel strained when you are around your relative?	0	1	2	3	4
10	Do you feel your health has suffered because of your involvement with your relative?	0	1	2	3	4
11	Do you feel that you don't have as much privacy as you would like because of your relative?	0	1	2	3	4
12	Do you feel that your social life has suffered because you are caring for your relative?	0	1	2	3	4

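### A between-arm comparison of carer burden and QoL is planned, but no control-arm carers are, and the ZBI described (22 items) differs from the form printed (12 items)

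*Combined protocol and SAP*

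**What the plan says.** Section 3.7, question 4, lists for carers "For Carers: Comparison of QoL and ZARIT (before and after"), with two contrasts beneath it: "between groups (EG Vs CG") and within the EG. Section 3.4 puts "Reduction/stability of informal caregiver's burden" among the informal-caregiver outcomes. For formal caregivers it lists one outcome only, quality of work.

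Table 2 plans informal caregivers at 20-22 in Italy, 20-23 in Switzerland and 8-10 in Norway. The three figures for seniors with MCI are the same. The control group is a single cell, "≥30 (≥10 per each pilot site"), with no carer column beside it. Section 3.1 says that "the 80 subjects are randomly assigned to the" experimental or control group. Section 3.6.1 gives control members a booklet and adds: "They will be evaluated at T0 and at T6 like the EG". It does not mention their carers.

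On the instrument, section 3.5 says the ZBI "is a caregiver self-report measure [9], containing 22 items", each scored 0 to 4. Table 6 schedules it at T0 and T2 for informal and formal caregivers under one heading, with no arm named. Annex 3 prints the form four times (formal and informal caregiver, T0 and T2). Each copy is numbered 1 to 12 and ends at the same question: "Do you feel that your social life has suffered because you are caring for your relative"? Table 6 gives carers the EQ-5D-5L. Section 3.7 says only QoL.

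**The concern.** A between-arm contrast needs carers in both arms. If sites recruit to Table 2, carers exist only for EG seniors and one side of the section 3.7 comparison is empty. What remains is a six-month change in EG carers. That change cannot be separated from natural drift or from regression to the mean, although section 3.7 promises a controlled result on burden.

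The score is also undefined. The text and the forms imply different totals on different ranges, so a reported ZBI mean could not be interpreted without knowing which version was used. In addition, the items ask about 'your relative' and are given to psychologists, neurologists, occupational therapists and nurses, for whom they do not fit.

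**Working it through.** **Whom Table 2 counts.** Inputs are the Table 2 cells and the 80 subjects of section 3.1.

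- EG seniors: 20 + 20 + 8 = 48 to 22 + 23 + 10 = 55.
- Informal caregivers: the same sums, 48 to 55, equal to the seniors at every site.
- Control group: at least 30.

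The stated 80 can be set against four readings of the table, taking the control cell at its minimum of 30:

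| Reading | Total |
|---|---|
| Senior column is the EG; control cell is all seniors | 48 + 30 = 78 to 55 + 30 = 85 |
| Control cell is 15 seniors and 15 carers (seniors counted) | 48 + 15 = 63 to 55 + 15 = 70 |
| Senior column already covers both arms | 48 to 55 |
| Everyone counted: seniors, carers, controls | 96 + 30 = 126 to 110 + 30 = 140 |

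Only the first contains 80 (50 EG + 30 CG). The control cell is therefore best read as seniors, and the 48-55 planned carers pair one to one with the EG. One carer per senior in both arms would need at least 30 more, that is 78-85 instead of 48-55.

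**What can be estimated.** With 48-55 carers in the EG and none planned in the CG, the within-EG change is estimable and the EG-versus-CG difference is not.

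**ZBI range.** Maximum = items × 4.

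- Section 3.5: 22 × 4 = 88.
- Annex 3: 12 × 4 = 48, from 12/22 = 55% of the items described.
- A carer answering 2 throughout scores 22 × 2 = 44 on one version and 12 × 2 = 24 on the other.

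**What a controlled carer comparison could show.** The documents give no alpha, power, effect size, SD or dropout for any outcome. The following assumes two-sided alpha 0.05, 80% power and no dropout. The detectable standardised difference is (1.960 + 0.842) × √(1/30 + 1/n):

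- n = 48: 2.802 × √0.05417 = 0.65
- n = 55: 2.802 × √0.05152 = 0.64

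Power for a difference of 0.5 SD is about 57% to 60%. These figures do not take account of baseline adjustment, and the conclusion does not rest on them.

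**The case against.** The strongest reply is that the documents are silent on control carers and do not exclude them. Section 3.7 itself names the contrast. Section 3.6.1 has controls evaluated like the EG, Table 6 names no arm, and the eligibility criterion for informal caregivers is not tied to an arm. Table 2 is not a full list of respondents either: for formal caregivers it gives centres, not people. Finally, the control figure is a floor, and agreement with 80 shows who is randomised, not whose carers are measured. All of this stands, and it limits the claim. A reader might infer that the comparison is impossible or that control carers are ruled out, and no section says so. The gap is that no target, source or procedure exists for one side of a stated contrast.

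On the instrument, 12 items may be a deliberate short form. Since the T0 and T2 copies are identical, change scores would be comparable within the trial. That also stands, so the mismatch does not by itself block an analysis. Loss in text extraction cannot be fully excluded but is unlikely: four copies stop at the same item, and the scales after them are complete (20-item UCLA, 14-item WEMWBS).

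Three further inferences are not supported. A reader might think a 22-item reference value would be misapplied, but the plan uses no ZBI cutoff. A reader might think formal and informal carers are to be pooled. Table 6 shares one schedule between them, but no pooled analysis is stated, and section 3.4 assigns burden to informal caregivers. A reader might also see an error in the absence of QoL-AD from the carer forms. Section 3.7 says only QoL for carers, and EQ-5D-5L is already scheduled, so only the label is missing.

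Finally, this is a pilot with MAC-Q as its primary outcome and caregiver benefit ranked second. The primary comparison is untouched.

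**Conclusion.** The point holds in a limited form. As recruitment is planned, there are 48-55 carers for the EG and no stated provision for CG carers, so the carer comparison reduces to an uncontrolled before/after change. This rests on reading the control cell as seniors, the only one of the four readings that agrees with 80 randomised. It also rests on sites recruiting what Table 2 lists.

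The ZBI conflict is direct: 22 items and 0-88 in section 3.5, against 12 items and 0-48 on all four forms. So is the mismatch between scheduling the ZBI for formal caregivers and section 3.4, which gives them no burden outcome. These matters should be corrected before carer data are collected. They concern non-primary outcomes and do not threaten the primary analysis.

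**What to change.** 1. **Carer contrast.** The simpler course is to delete the between-group line for carers in section 3.7 and report carer results as uncontrolled within-EG change. It costs a wording change and a weaker claim. Alternatively, where sites can manage it, recruit and consent the primary informal caregivers of control seniors, have them complete the existing T0 and T2 forms, and add a control-carer row to Table 2. Section 4.1 would then need a baseline-adjusted model, for example T2 score on arm with T0 score as covariate. It contains none now, only descriptive statistics, Mann-Whitney and chi-square tests, and correlations. The cost is about 30 more people to recruit, consent and follow at two time points. Norway needs particular attention, because section 4.3.3 limits its data to matters directly connected with improving the technology.
2. **ZBI version.** Make section 3.5 and all four annex forms agree on one version, and state the item count and score range (22 items, 0-88, or 12 items, 0-48). The 22-item form adds ten questions per administration. The 12-item form needs only a change of text.
3. **ZBI respondents.** Administer and analyse it for informal caregivers only, remove it from the formal-caregiver forms, and split Table 6 accordingly. This reduces burden on staff.
4. **Carer QoL.** Name the EQ-5D-5L already scheduled in Table 6 as the carer measure in section 3.7. This costs nothing.

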## 4 Data Management

#### 4.1 Statistical Analysis

The first step of the data analysis will deal with the description of the sample. Continuous variables will be reported as either mean and standard deviation or median and interquartile range on the basis of their distribution (assessed using Kolmogorov-Smirnov test). Categorical variables will be expressed as an absolute number and percentage. Mann-Whitney U tests (for non-normal distribution), or Chi-Square tests (normal or non-normal) will be used to compare the independent and dependent variables between the pre- and post- conditions, in addition to simple descriptive statistics (means, medians and SDs as appropriate).

In order to verify the achievement of the primary endpoint (i.e., MAC-Q), subscales of the questionnaire will be calculated. Means and standard deviation or medians and iqr of the scores will be reported according to their distribution. Correlation coefficients (Pearson for normally distributed variables, Spearman for non-normally distributed variables) of the sub-scales with the other rating scales at each stage of the study and with the main characteristics of the subjects will be calculated to check for potential determinants of higher acceptability.

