The **Reisberg Scale** [2] consists of 7 major clinical stages. It is used by clinicians and in care settings, but may be especially helpful for caregivers, as it is noticeably detailed regarding the general abilities of an individual at each stage and provides information about what to expect at different stages. The scores go from no cognitive decline (1) to very severe cognitive decline (7), through stages 2, 3, and 4 that are respectively: Very mild cognitive decline (age-associated memory impairment), mild cognitive impairment, and moderate cognitive decline.

The **4-items Geriatric Depression Scale (GDS)** [3] is a 4-items scale whose answers are yes or no. If all the items are answered negatively then the depression is excluded; if only one item is answered positively then the situation is uncertain; if at least 2 items are answered positively, the patient is depressed. Thus, this scale is easy and quick, and very useful in excluding depression.

The **Memory Assessment Clinics – Questionnaire (MAC-Q)** [4] is a 6-item scale that uses a 5-item Likert scale from "much better now"=1 to "much worse now"=5, and the last question scores double. The questionnaire asks the person to compare his or her memory with a previous period to measure age-related memory decline. Five items address specific situations frequently reported as problematic by those who experience memory loss with age. One item is a global item assessing general memory decline. A cutoff of 25 points or more indicates that the individual has a memory disorder.

**Clinical Frailty Scale (CFS).** [5] This descriptive scale divides the older participants into 9 classes based on the information provided by them and their relatives: between 1 and 3 the patient is non-frail, pre-frail if 4, he is frail from 5 to 9.

The **UCLA scale** [10] is a 20-item scale designed to measure one's subjective feelings of loneliness as well as feelings of social isolation. Participants rate each item as either O ("I often feel this way"), S ("I sometimes feel this way"), R ("I rarely feel this way"), N ("I never feel this way").

**EQ Visual Analogue Scale (EQ VAS)** [11] records the respondent's self-rated health on a 20 cm vertical, visual analogue scale with end-points labelled 'the best health you can imagine' and 'the worst health you can imagine'. This information can be used as a quantitative measure of health as judged by the individual respondents.

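### Section 4.1 lets a normality check steer the analysis, but the tests it names do not fit the scores and none is assigned to the EG-CG comparison of MAC-Q

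*Combined protocol and SAP*

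**What the plan says.** Section 3.4 names the endpoint: "Primary outcome: perceived stability of cognitive status (MAC-Q"). Section 3.7 asks for a before-and-after comparison of MAC-Q, both between EG and CG and within EG.

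Section 4.1 (Statistical Analysis) gives the rules:

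- **Summaries.** "Continuous variables will be reported as either mean and standard deviation or median and interquartile range". A normality check makes the choice: it is made "on the basis of their distribution (assessed using Kolmogorov-Smirnov test"). No variant of the test, significance level or software is given.
- **Tests.** "Mann-Whitney U tests (for non-normal distribution), or Chi-Square tests (normal or non-normal) will be used". Both tests are given a single purpose, namely that they should "compare the independent and dependent variables between the pre- and post- conditions".
- **Correlations.** "Pearson for normally distributed variables, Spearman for non-normally distributed variables".
- **Primary endpoint.** Sub-scales of MAC-Q will be calculated, again summarised according to their distribution. The sub-scales are not defined.

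No t-test, paired test, signed-rank test, ANOVA, ANCOVA or mixed model is named anywhere in the document.

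**The concern.** A reader who follows section 4.1 for the primary outcome cannot reach a suitable test by any route. If MAC-Q is judged normal, the only test left is chi-square, which compares category counts and not score levels. If it is judged non-normal, the test is Mann-Whitney, which treats the two sets of scores as coming from different people, although the stated contrast is pre versus post in the same people. The contrast that uses the randomisation, EG against CG, has no test at all.

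At stake is a primary analysis that is either weaker than the data allow or chosen after the data are seen. There is also a smaller worry. Recruitment MAC-Q is cut by the entry rule and T2 MAC-Q is not, so the check can put the two time points in different branches and they would then be summarised differently.

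**Working it through.** The plan has no power or sample-size figure to reproduce. It gives no MAC-Q mean, SD or pre/post correlation, and no significance level, so these are assumed below and the test level is taken as 5%.

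**Step 1. What each branch leads to (sections 4.1 and 3.7)**

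| Contrast | Score judged normal | Score judged non-normal |
|---|---|---|
| Pre vs post, same people | chi-square only | Mann-Whitney (independent samples) |
| EG vs CG on MAC-Q | none assigned | none assigned |

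This step needs no assumption.

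**Step 2. Cost of an independent-samples test on paired scores**

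Inputs: n = 50 in EG (80 subjects in section 3.1, less the 30 controls in Table 2; the Table 2 targets for EG add to 48 to 55). Assumed: SD σ = 3, change δ = 1 point, pre/post correlation ρ = 0.5, 0.7, 0.8.

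A normal approximation shows the mechanism. An independent-samples test takes the variance of the mean difference as 2σ²/n, but for paired scores it is 2σ²(1 − ρ)/n. Hence:

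- Type I error ≈ 2Φ(−1.96/√(1 − ρ)). At ρ = 0.5 this is 2Φ(−2.77) = 0.6%; at 0.7 and 0.8 it is below 0.1%.
- Unpaired signal: δ/(σ√(2/n)) = 1/(3 × 0.2) = 1.67, below 1.96. Power ≈ Φ((1.67 − 1.96)/√(1 − ρ)) = 34%, 30%, 26%.
- Paired signal: δ√n/(σ√(2(1 − ρ))) = 2.36, 3.04, 3.73. Power ≈ Φ(signal − 1.96) = 65%, 86%, 96%.

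Simulation of the rank tests themselves (3,000 samples per setting):

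| ρ | Mann-Whitney type I | Wilcoxon type I | Mann-Whitney power | Wilcoxon power |
|---|---|---|---|---|
| 0.5 | 0.6% | 5.0% | 30% | 61% |
| 0.7 | 0.0% | 4.9% | 29% | 83% |
| 0.8 | 0.0% | 5.0% | 24% | 94% |

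A separate run gave 0 to 0.8% type I error and 27 to 31% power for Mann-Whitney, and 61 to 93% power for Wilcoxon. The misfit makes the test too conservative; it does not produce false positives.

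**Step 3. How stable the normality check is (secondary)**

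MAC-Q "is a 6-item scale that uses a 5-item Likert scale" with the last item counted double, so totals are integers from 5 × 1 + 2 = 7 to 5 × 5 + 10 = 35. Entry requires at least 25 (section 3.2.4), and Table 5 shows recruitment as the only pre-treatment MAC-Q. It can therefore take only 35 − 25 + 1 = 11 values.

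The 5% critical distances with mean and SD estimated from the sample, uncorrected against Lilliefors-corrected, are 0.242 vs 0.162 (n = 30), 0.188 vs 0.125 (n = 50) and 0.150 vs 0.099 (n = 80). A distance between the two counts as normal under one and non-normal under the other. Simulated recruitment scores (rounded normal cut to 25-35, 1,000 samples per setting; the mean and SD are those before the cut):

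| Assumed mean, SD | n | Uncorrected rejects | Lilliefors rejects | Disagree |
|---|---|---|---|---|
| 26, 4 | 30 | 3% | 63% | 60% |
| 26, 4 | 50 | 16% | 92% | 76% |
| 26, 4 | 80 | 57% | 99% | 43% |
| 28, 4 | 30 | 1% | 39% | 38% |
| 28, 4 | 50 | 4% | 68% | 65% |
| 28, 4 | 80 | 19% | 91% | 73% |

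Over a wider assumed range (mean 24 to 30, SD 3 to 4) disagreement runs from 11% to 76%. For T2 scores, which have no entry cut, it runs from 14% to 54%.

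**The case against.** Several points on the other side stand.

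- **Chi-square.** The phrase probably means chi-square for categorical data, where normality is irrelevant. A reader might infer that the plan intends chi-square on MAC-Q scores. The text does not go that far; what it shows is that no parametric test is named.
- **Reach of the check.** Kolmogorov-Smirnov is tied in words only to the choice of summary. That it also picks the test and the correlation is an inference, though no other normality check is named.
- **Effect of the variant.** A reader might infer that the software decides the primary result. That is not supported. In a simulation of T2 MAC-Q with 50 vs 30 participants, assuming a t-test fills the normal branch, the variants disagreed on normality in 52 to 58% of samples, yet significance differed in only 1 to 4%, and type I error was 4.7 to 4.9% under either. Nor does the uncorrected version almost never reject: it reaches 57% at n = 80 in the table above.
- **Sub-scales.** If these behave like single 1-5 items, both variants reject almost always at n of 50 or more, and the disagreement disappears.
- **Summaries.** Section 4.1 also allows means, medians and SDs as appropriate, so both summaries can be reported.
- **Pilot status.** Section 3.1 calls the trial a pilot with only a partial evaluation of effectiveness.

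Mann-Whitney would be valid for EG vs CG, but section 4.1 does not assign it there and does not say whether T2 scores or changes would be compared. None of this supplies a suitable test for paired scores or for the group contrast.

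**Conclusion.** The point holds as a mismatch between tests and scores. That part rests on the text alone: no suitable test is named for a score judged normal, an independent-samples test is assigned to paired data, and nothing is assigned to EG vs CG on the primary outcome.

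The size is conditional. With SD 3, n = 50 and correlation 0.5 to 0.8, following the plan gives type I error under 1% and about 24 to 31% power for a 1-point change, where a signed-rank test has 61 to 94%. The power simulation ignores the entry cut, and the loss shrinks if the true correlation is lower.

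The instability of the normality check is real but secondary. Its rates depend on assumed MAC-Q distributions, and it may seldom alter a between-group conclusion. The pilot setting lowers the stakes, so this should be corrected but is not a fatal fault.

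**What to change.** Delete the normality gate from section 4.1 and set the methods in advance:

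- **EG vs CG:** a linear model for T2 MAC-Q total, adjusted for recruitment MAC-Q (ANCOVA), with a rank-based or bootstrap analysis as sensitivity.
- **Within EG:** one named paired test, paired t or Wilcoxon signed-rank.
- **Correlations:** Spearman throughout.
- **Chi-square:** categorical variables only.
- **Summaries:** mean (SD) and median (IQR) for each scale at both time points.

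The cost is SAP wording and slightly longer tables. No extra participants, visits or data are needed.

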## 3 Field trial

#### 3.1 Study design

The field trial will be conducted as a controlled longitudinal study, with a before and after design where the observations are made on a series of enrolled individuals, receiving the intervention described below with control group, with data collected before and after the installation and use of the technical solution. The goal of trial evaluation is to assess the engAGE technology integration into everyday life, effectiveness on mitigating the cognitive decline, acceptance over six months, security and reliability of proposed solutions as well as the business perspective reflecting the market demand (including the willingness to pay) for the developed services. The field trial procedure will be divided into two different phases, after the recruitment of the participants: Baseline evaluation (T0, M1) and Final evaluation (T1, M6), with the aim of collecting data as follows:

- **Recruitment phase** (R): the recruitment protocol will include general information on the subjects, in particular, health status and cognitive condition. The information will be collected with the help of the caregiver/family member if needed.
- **Baseline evaluation** (T0, M1): that will consist of the first real contact with the users and their families, before the start of the field trial.
- **Mid-term evaluation** (T1, M3): the aim of mid-term evaluation is to collect useful information on the use of the engAGE platform after a short period of use for detecting and analysing the technology acceptance and usability issues.
- Final evaluation (T2, after six months of use, M6): the aim of this phase is to collect useful information on the whole benefits perceived by the users after a meaningful period of use of the system. The final evaluation will be conducted after the system de-installation, to detect and analyse the impact of the system in the daily life of the older people and their family. Moreover, the final evaluation aims to gain knowledge on elderly technology acceptance and usability issues to be compared with mid-term results (T1), in order to assess the longterm acceptance and provide methodological approach for further studies in the field.

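### Section 4.1 assigns independent-samples tests to paired pre/post scores, so the before/after p-values are invalid (too large if scores correlate positively) and real change can be missed

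*Combined protocol and SAP*

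**What the plan says.** Section 4.1 names the tests for comparing outcomes in one sentence, which begins "Mann-Whitney U tests (for non-normal distribution), or Chi-Square tests (normal or non-normal) will be used to compare". What is compared is given as "the independent and dependent variables between the pre- and post- conditions", alongside descriptive statistics. The contrast is before versus after. EG versus CG is not mentioned in that sentence or anywhere else in 4.1. For the primary endpoint, 4.1 adds only subscale summaries and correlations.

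Section 3.1 describes a controlled before-and-after study "with data collected before and after the installation and use of the technical solution". Table 5 schedules MAC-Q at recruitment (R) and T2, and WEMWBS and QoL-AD at T0 and T2. Table 6 schedules the Zarit interview (ZBI) at T0 and T2. Section 3.7 plans before/after comparisons of MAC-Q, quality of life, WEMWBS and Zarit, each both between groups and within EG. Section 3.4 gives the "Primary outcome: perceived stability of cognitive status (MAC-Q"). On allocation, 3.1 says that "the 80 subjects are randomly assigned to the" experimental or control group.

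**The concern.** A before/after comparison within EG uses two scores per person. Mann-Whitney U and the ordinary chi-square test treat the two sets of scores as if they came from different people. When a person's scores are positively correlated, the change varies less than the test assumes. The p-value is then too large and the test rejects too rarely.

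That direction matters here because the primary outcome is stability, and for informal caregivers section 3.4 counts stable burden as a success. A test that rejects too rarely can miss a real decline, and the non-significant result can then be read as the hoped-for stability.

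The sentence has a second gap. Mann-Whitney is reserved for non-normal data, so a normally distributed scale score is left with chi-square, which does not analyse a continuous score.

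**Working it through.** The documents give no significance level, power, effect size, SD or correlation for these tests, so there is no stated figure to reproduce.

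**Inputs from the documents**
- EG size, Table 2: 20 + 20 + 8 = 48 up to 22 + 23 + 10 = 55.
- CG size, Table 2: at least 30. EG and CG together come to at least 78 to 85, compatible with the 80 in section 3.1.

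**Assumptions**
- Two-sided 5% level, equal SD before and after, no dropout, n = 48 pairs.
- Mean change d = 0.2 to 0.5 SD.
- Pre/post correlation r = 0 to 0.8.

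**Formulas (normal approximation)**
- True variance of the mean change: 2·SD²·(1 − r)/n. An unpaired test uses 2·SD²/n, so its statistic has true SD √(1 − r) instead of 1.
- Real type I error of the unpaired test: 2·Φ(−1.96/√(1 − r)).
- Power of the unpaired test: Φ((d/√(2/n) − 1.96)/√(1 − r)).
- Power of the paired test: Φ(d/√(2(1 − r)/n) − 1.96).

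**Worked case, n = 48, d = 0.3, r = 0.5**
- d/√(2/48) = 0.3/0.2041 = 1.470, and √(1 − r) = 0.7071.
- Type I error: 2·Φ(−2.772) = 0.0056.
- Unpaired power: Φ(−0.490/0.7071) = Φ(−0.693) = 0.244.
- Paired power: Φ(1.470/0.7071 − 1.96) = Φ(0.119) = 0.547.

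**Simulation with the rank tests themselves** (n = 48, 5000 runs per cell; MW = Mann-Whitney, SR = Wilcoxon signed-rank)

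| r | Type I error, MW / SR | Power d=0.2, MW / SR | d=0.3 | d=0.4 | d=0.5 |
|---|---|---|---|---|---|
| 0 | 5.0% / 4.6% | 15% / 15% | 29% / 28% | 48% / 47% | 65% / 65% |
| 0.3 | 2.2% / 4.9% | 13% / 21% | 27% / 39% | 46% / 61% | 69% / 80% |
| 0.5 | 0.7% / 4.7% | 8% / 27% | 24% / 51% | 47% / 76% | 72% / 90% |
| 0.7 | 0.04% / 4.6% | 4% / 40% | 19% / 73% | 46% / 93% | 76% / 99% |
| 0.8 | 0.02% / 4.9% | 2% / 55% | 15% / 87% | 46% / 99% | 81% / 100% |

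The smallest type I errors rest on very few rejections: 0.04% is 2 in 5000. A longer null run of 40,000 at n = 48 gave 2.1% (r = 0.3), 0.6% (r = 0.5) and 0.1% (r = 0.7; 46 rejections). The normal approximation gives 1.9%, 0.6% and 0.03%. At r = 0.7 only the order of magnitude is firm.

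**Share of signed-rank power lost by using Mann-Whitney,** (SR − MW)/SR from unrounded values

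| r | d=0.2 | d=0.3 | d=0.4 | d=0.5 |
|---|---|---|---|---|
| 0.3 | 41% | 31% | 25% | 15% |
| 0.5 | 70% | 53% | 38% | 21% |
| 0.7 | 90% | 74% | 51% | 23% |

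With 55 pairs the normal approximation shows the same pattern: at r = 0.5 the losses are 69%, 52%, 32% and 14%.

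**Effect of the entry rule.** Section 3.2.4 requires MAC-Q ≥ 25, which narrows the baseline range and lowers r for the primary outcome. With an assumed population mean of 26 and SD of 4, a population correlation of 0.7 falls to about 0.53 among those enrolled, and 0.5 falls to about 0.35. For MAC-Q, the r = 0.3 and r = 0.5 rows may therefore be nearer the mark than the lower rows.

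**The case against.** The strongest reply is that the wording is loose and the authors may have meant Mann-Whitney for EG versus CG, where it would be valid. The text says before versus after, however. If the other meaning was intended, the within-EG comparisons in 3.7 have no test at all, so the sentence needs changing either way.

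A second reply is that section 3.1 calls this a pilot, run mainly to learn whether the services are useful and usable, with only a partial evaluation of effectiveness. A conservative error in an uncontrolled comparison is also less harmful than a false positive. This limits the consequences, but 3.7 still plans these comparisons, and a small sample can ill afford lost power.

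Four stronger readings are tempting, and the documents do not support them:
- *Most within-group power is lost.* In the cases examined, more than half is lost only at r of about 0.5 or more with d of about 0.3 or less, or at r of 0.7 to 0.8 with d up to about 0.4. At r = 0.3, or at d = 0.5, the loss stays below half.
- *The p-values produce false positives.* With positive correlation the error runs the other way.
- *Scales will be cut into categories for chi-square.* The preceding sentence in 4.1 concerns categorical variables, so chi-square may be meant only for those. What can be said is that no suitable test is named for normally distributed scores.
- *These are the only tests in 4.1.* It also names Kolmogorov-Smirnov and correlation coefficients. The two criticised tests are the only ones named for comparing outcomes.

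**Conclusion.** The point holds. Section 4.1 assigns independent-samples tests to paired data, and no paired method is named anywhere. The before/after p-values are invalid whenever the two scores are correlated, and conservative when the correlation is positive.

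The size is conditional. For 48 pairs at an assumed two-sided 5% level, the real type I error is about 2% at r = 0.3, 0.7% at r = 0.5 and 0.04% to 0.1% at r = 0.7. At an assumed 0.3 SD change, Mann-Whitney gives up 12, 27 and 54 percentage points of power (39 − 27, 51 − 24, 73 − 19). At r = 0 there is no loss. The correlation, effect size and significance level are assumptions, and so is the absence of dropout, so no single figure for the loss should be quoted as fact.

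The same sentence leaves two further gaps: no suitable test for normally distributed scale scores, and no test for EG versus CG. The second is the randomised contrast, the one that can support a claim of effect.

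**What to change.** Replace the sentence in 4.1 with wording that separates the two contrasts:

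- **Within group, pre versus post:** paired t-test or Wilcoxon signed-rank test according to the distribution of the change, reporting the mean or median change with a 95% CI. Use McNemar's test for paired binary items.
- **Between groups, EG versus CG:** compare the T2 score adjusted for baseline (ANCOVA), or use Mann-Whitney on change scores if the distribution is non-normal. Name the baseline visit (R for MAC-Q; T0 for WEMWBS, QoL-AD and ZBI), and align the visit labels, since section 3.6.1 calls the control group's final assessment T6.
- **Chi-square:** only for categorical variables compared between independent groups.

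State the significance level and sidedness, and say that a non-significant before/after test will not by itself be taken as evidence of stability; the confidence interval for the change should be shown.

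The cost is a few lines of wording. The recruitment, T0 and T2 forms for seniors in Annex 3 carry a subject identification code, so scores can be paired without new data.
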